##### *Missing day only*

- If the month and year are the same as the year and month of first dosing date, then the first dosing date will be assigned to the missing day.
- If the year of the partial date is before the year of the first dosing date or the year of the partial date and the first dosing date are the same but the month of partial date is

before the month of the first dosing date, then the last day of the month will be assigned to the missing day.

- If either the year of the partial date is after the year of the first dosing date or the year of the partial date and the first dose date are the same but the month of partial date is after the month of the first dosing date, then the first day of the month will be assigned to the missing day.
- If the stop date is not missing, and the imputed start date is after the stop date, the start date will be imputed by the stop date.

*Missing day, month, and year*

- No imputation is needed.

**Incomplete End Date:**

If the imputed stop date is before the start date, then the imputed stop date will be equal to the start date.

*Missing day and month*

- If the year of the incomplete stop date is the same as the year of the last dosing date, then the day and month of the last dosing date will be assigned to the missing fields.
- If the year of the incomplete stop date is prior to the year of the last dosing date or prior to the year of the first dosing date, then December 31 will be assigned to the missing fields.
- If the year of the incomplete stop date is prior to the year of the last dosing date but is the same as the year of the first dosing date, then the first dosing date will be assigned to the missing date.
- If the year of the incomplete stop date is after the year of the last dosing date, then January 1 will be assigned to the missing fields.

*Missing day only*

- If the month and year of the incomplete stop date are the same as the month and year of the last dosing date, then the day of the last dosing date will be assigned to the missing day.
- If either the year of the partial date is not equal to the year of the last dosing date or the year of the partial date and the last dosing date are the same but the month of partial date is not equal to the month of the last dosing date, then the last day of the month will be assigned to the missing day.

*Missing day, month, and year*

- No imputation is needed.

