### 10.3.1. Treatment-emergent Adverse Events

An AE is defined as a treatment emergent adverse event (TEAE) if it meets one or more of the following criteria:

- An AE starting on or after the first study drug dose and within 30 days after the last dose of study drug.

- An AE occurring prior to the first study drug dose that worsens (increase in grade) after the first study drug dose.

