#### 10.3.4. TEAE Analyses

The counts and percentages of subjects experiencing a TEAE and TEAEs by PTs and SOCs in the following categories will be presented by study treatment arm:

All AE summaries will be restricted to TEAEs. Each AE summary will be displayed by treatment group for DB phase, DBext phase, and combined. Summaries that are displayed by SOC and PT will be ordered by descending order of incidence of SOC and PT within each system organ class.

Summary tables of the following TEAEs will be presented:

- Overall summary of TEAEs
- Patient incidence of TEAEs and the total number of entries by SOC and PT. This summary will be repeated for subgroups specified in [Section 10.10](#).
- Patient incidence of TEAEs by SOC, PT, and highest severity. At each level of patient summarization, a patient is classified according to the highest severity if the patient reported 1 or more events. AEs with missing severity will be considered severe for this summary.
- Patient incidence of TEAEs by SOC, PT, and closest relationship to IP (Related/Not Related). Related AEs are those with relationships reported as “Definite,” “Probable,” or “Possible,” and unrelated AEs are those with relationships reported as “Unlikely” or “Not Related”. At each level of patient summarization, a patient is classified according to the closest relationship if the patient reported 1 or more events. AEs with a missing relationship will be considered related for this summary.
- Patient incidence of serious TEAEs and the total number of entries by SOC and PT.
- Patient incidence of TEAEs leading to IP withdrawal or study discontinuation by SOC and PT. This is a subset of the AEs where Action Taken with Study Treatment is checked as “Drug Withdrawn” or where “Patient Discontinued from Study” is checked on the eCRF.
- Patient incidence of COVID-19 related TEAEs.

Patient incidence will be summarized as subject counts and percentages unless otherwise specified.

The number of AEs and events per 100 patient years will be summarized by SOC and PT.

- Individual patient years = (the last recorded study visit date – first dose date +1)/365.25  
where: the last recorded study visit date = end of study date recorded on end of study CRF page for that patient
- Total patient years on study = sum of all individual patient years within the Safety Population
- Events per 100 patient years =  $\frac{\text{Number of Event} \times 100}{\text{Total Patient Years on Study}}$

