### 10.3.5. Pruritus Adverse Events

Pruritus: Treatment-emergent pruritus, defined as any PT including “Prur” will be summarized separately by the treatment group, SOC, and PT as a subset of all TEAEs. This summary will be repeated for subjects with “new or worsened” pruritus events, as defined as follows:

- Mild, moderate, or severe treatment-emergent pruritus events in patients with no pruritus at baseline, or
- Worsening of the severity of the baseline condition in patients with pruritus at baseline.

Baseline pruritus is defined as the Investigator’s rating of severity as collected on the PBC Disease History eCRF. Patients whose baseline severity is severe will be counted as worsening if an AE of pruritus with severe is recorded.

An analysis of treatment-emergent pruritus event days per patient years on study will be performed. The days at each severity grade, including the total days of event, the total patient years on study, and the event days per patient year on study at each severity grade, including the total, will be summarized.

In order to explore the relationship between pruritus and the IP, the following time-to-event analyses will be performed:

- Time to first onset of treatment-emergent pruritus

The time to the start of the first episode = date of onset of first episode – date of first dose of IP + 1.

Patients who never reported an AE of pruritus will be censored at the date of last contact.

- Time to onset of the first moderate or severe treatment-emergent pruritus

The time to the start of the first moderate or severe pruritus = date of onset of the first moderate or severe pruritus – date of first dose of IP +1.

Patients who never reported a moderate or severe AE of pruritus will be censored at the date of completion or discontinuation.

- Time to onset of the first severe treatment-emergent pruritus

The time to the start of the first severe pruritus = date of onset of the first severe pruritus – date of first dose of IP +1.

Patients who never reported a severe AE of pruritus will be censored at the date of completion or discontinuation.

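### Two rules for a year-only adverse-event stop date overlap and give different dates; one of them reduces any event that starts after first dose to a single day

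*SAP*

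**What the plan says.** Appendix A, Incomplete End Date, has four bullets for a stop date with day and month missing. The two that matter here are:

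- **Second bullet.** If the stop year is before the year of the last dose, "or prior to the year of the first dosing date, then December 31 will be assigned to the missing fields".
- **Third bullet.** If the stop year is before the last-dose year but is the "same as the year of the first dosing date, then the first dosing date will be assigned to the missing date".

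A general rule stands above the bullets: "If the imputed stop date is before the start date, then the imputed stop date will be equal to the start date". For a date missing entirely, start or stop, the appendix says "No imputation is needed".

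Stop dates feed a named analysis. Section 10.3.5 states: "An analysis of treatment-emergent pruritus event days per patient years on study will be performed", by severity grade and in total. Section 10.3.6 plans the same for fatigue. Section 10.3.4 defines patient-years as running from first dose to the end-of-study date.

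**The concern.** Imputation rules should give one answer for each incomplete date. Here the third bullet's condition is wholly contained in the second's, and the two assign opposite ends of the on-treatment part of the year. Two programmers following the text could build different datasets.

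The third bullet is also a poor rule taken alone. It places the stop on the first day of dosing, which precedes the onset of any event that starts later. The stop is then moved up to the start, and the event is left with the shortest possible duration. Safety and tolerability is a primary objective, and pruritus and fatigue burden per patient-year are planned outputs, so the choice should be fixed before database lock.

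**Working it through.** The SAP states no figure to reproduce. The check applies the rules literally.

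**1. Overlap.** Let Y be the stop year, F the first-dose year and L the last-dose year.
- Second bullet: Y < L (or Y < F) gives 31 December of Y.
- Third bullet: Y < L and Y = F gives the first dosing date.

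The third condition implies the second. Both apply exactly when Y = F and F < L. Running all four bullets over every first-dose day of a 365-day year, with dosing lengths from 84 to 1,095 days, found no conflict in any other stop year and no stop year left without a rule.

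**2. Size in one patient (illustrative dates).** First dose 1 March 2019, last dose 31 January 2020 (337 days inclusive), pruritus from 10 April 2019, stop recorded only as 2019. Duration is taken as stop − start + 1.
- Second bullet: stop 31 December 2019. Days = 21 (April) + 31 + 30 + 31 + 31 + 30 + 31 + 30 + 31 = 266.
- Third bullet: stop 1 March 2019, before onset, so it is reset to 10 April 2019. Days = 1.

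The second result is general. For any onset after first dose, the third bullet's date precedes the start, so stop = start and the duration is 1 day. If the start is also known only to the year, and that year is the first-dose year, the start rules set onset to the first dosing date. The third bullet then leaves a one-day event on Day 1.

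**3. How many first-dose dates allow the conflict.** Section 3 gives at least 48 weeks of treatment, 48 × 7 = 336 days. With first dose on day k of a 365-day year, the last dose falls on day k + 335. That is in the next year when k + 335 > 365, so k runs from 31 to 365: 335 values. For k = 365 both bullets give 31 December, which leaves 334 with different dates: 334/365 = 91.5%. The gap is 365 − k days, from 1 to 334, mean (1 + 334)/2 = 167.5.

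| Days of dosing | First-dose days with two different dates | Share |
|---|---|---|
| 84 | 82 of 365 | 22.5% |
| 168 | 166 of 365 | 45.5% |
| 336 | 334 of 365 | 91.5% |
| 504 or 1,095 | 364 of 365 | 99.7% |

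These shares assume uniform first-dose dates. They show where a conflict is possible, not how often it will occur.

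**4. Which outputs use a stop date.** TEAE incidence, severity, relationship, serious events, withdrawals and events per 100 patient-years (10.3.4) rest on occurrence. Time to onset of pruritus and fatigue (10.3.5, 10.3.6) rests on the start date. Among the named AE analyses, only the two event-day analyses need a stop.

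**5. Two neighbouring gaps.**
- *Ongoing events.* No end is stated for an event with no stop date. Pruritus from Day 85 still present on Day 336 covers 336 − 85 + 1 = 252 days if counted to Day 336. The SAP does not say whether it counts those days or none.
- *No start date.* The first TEAE criterion in 10.3.1 is "An AE starting on or after the first study drug dose and within 30 days after the last dose of study drug", which cannot be judged without a start date. The second concerns worsening of an event that began before first dose. No default is given, whereas 10.3.4 gives one for other missing items, for example "AEs with a missing relationship will be considered related for this summary".

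**The case against.** The best defence is that the third bullet is worded as a specific exception to the second, so a programmer would let it prevail and there would be only one answer. That may settle precedence, but it selects the worse rule: every affected event that starts after first dose then lasts 1 day.

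A second defence is scale, and it largely stands. The study tests no formal hypothesis, plans about 50 patients and makes no inferential safety comparison unless specified. With visits about every 6 weeks, stop dates known only to the year may be few. This is why the point is minor.

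A reader might also infer more than the SAP supports:

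- *That long-lasting events vanish from the safety summaries.* They do not. Ongoing pruritus or fatigue stays in incidence and time to onset. Nothing says its event days are set to zero; the end point is simply unstated.
- *That every defect understates harm.* The second bullet assigns the latest date in the year and does not shorten an event. The start rules are also cautious: a year-only start in the first-dose year becomes the first dosing date, which makes the event treatment-emergent.
- *That an event with no start date cannot be a TEAE.* It cannot be classified by the first criterion, but documented worsening after first dose could satisfy the second. No text orders exclusion, and the event stays in the listing of all AEs.
- *That most completers with a year-only stop date are affected.* The 91.5% is a share of first-dose dates. The stop year must also be the first-dose year, and treatment continues into an extension whose later stop years do not conflict.

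**Conclusion.** The second and third bullets for a year-only stop date contradict each other whenever the stop year is the first-dose year and dosing runs into a later year (unless first dose is on 31 December). The third bullet gives a wrong result even if it is read as an exception. The damage is confined to pruritus and fatigue event days. It can be large for one event (266 days against 1 in the example), but its total size is unknown because the SAP gives no frequency of such dates. The 334-of-365 figure rests on 336 days of dosing and uniform first-dose dates. Any difference between arms would depend on the data.

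The treatment of ongoing events and of events with no start date is a gap to close, not a contradiction. Severity: minor.

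**What to change.** Delete the third bullet for a stop date with day and month missing, so that 31 December applies whenever the stop year precedes the last-dose year. Each year-only stop date then has one answer.

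Add two clarifying sentences:

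1. In 10.3.5 and 10.3.6, count an event that is ongoing with no stop date up to the end date used for the patient-year denominator in 10.3.4.
2. In 10.3.1, classify an event with a fully missing start date as treatment-emergent unless its stop date is before first dose.

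Leave the other partial-date rules unchanged. Replacing them all with the latest date consistent with the known part would be a preference, and nothing here shows it is needed.

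The cost is a few lines of SAP text and programming before database lock. Some durations and TEAE counts may become slightly conservative. Listings already show the original dates, so imputed values remain traceable.

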## **Visit Windows**

Visit windows are specified in the Table 1 of the protocol - Schedule of Study Procedures for the 2 phases of the study: DB phase and DBext phase. All data will be tabulated per the evaluation visits as recorded on the electronic case report form (eCRF) even if the assessment is outside of the visit window. In data listings, the study day of all dates will be presented. Data collected at unscheduled visits that occurred outside the time windows specified will be included in the data listings but will not be included in the analyses unless otherwise stated.

## **Pooling of Centers**

Data from all study centers will be combined for analysis.
